8.5.4. TRC253 Study Drug Accountability

The Investigator must maintain an accurate accounting of TRC253 supplied by TRACON. During the study, the following information must be recorded:

- Date of receipt, quantity and lot number of the TRC253 study drug received from TRACON
- ID number of the patient to whom the product is dispensed
- The date(s) and quantity of the product dispensed
- Dates and quantity of product returned, lost or accidentally or deliberately destroyed

Investigational Drug Accountability Logs should be maintained by the site and must be readily available for inspection.

8.5.5. TRC253 Handling and Disposal

TRC253 must be stored at controlled room temperature. The Investigator should not return (nor destroy) clinical study materials to TRACON unless specifically instructed to do so by TRACON. See pharmacy manual for further instructions regarding handling and disposal.

9. CONCOMITANT MEDICATIONS

All therapies (prescription or over-the-counter medications, including vaccines, vitamins, herbal supplements; non-pharmacologic therapies such as electrical stimulation, acupuncture, special diets, exercise regimens, blood products) different from the study drug must be recorded in the eCRF beginning with 28 days prior to the first dose and for at least 28 days after the last dose. Recorded information will include a description of the type of the drug, treatment period, dosing regimen, route of administration, and its indication.

Concomitant therapies and any medications used to treat or support adverse events or serious adverse events must be recorded on the eCRF and in source documents throughout the study beginning with start of the first dose of study drug to 28 days after the last dose of study drug. The sponsor must be notified in advance (or as soon as possible thereafter) of any instances in which prohibited therapies are administered.

No other approved or investigational anticancer treatment will be permitted during the study period. No other investigational drug may be used during treatment on this protocol, and concurrent participation in another clinical trial is not allowed.

9.1. Permitted Medications

The following concurrent medications may be administered during the study:

- Standard supportive care therapies (antiemetics, antidiarrheals, anticholinergics, antispasmodics, antipyretics, antihistamines, analgesics, antibiotics and other antimicrobials, histamine receptor (H₂) antagonists or proton pump inhibitors, and other medications intended to treat symptoms or signs of disease) as clinically indicated, according to institutional standards and as deemed necessary by the investigator.
- Granulocyte colony stimulating factor and transfusions such as red blood cells and platelets are permitted to treat symptoms or signs of neutropenia, anemia, or thrombocytopenia; not allowed as prophylactic treatment during DLT period in Part 1.
- Documented infectious complication should be treated with oral or intravenous antibiotics or other anti-infective agents as considered appropriate by the treating investigator for a given infectious condition, according to standard institutional practice.
- GnRH analog therapy

9.2. Prohibited Medications

The following concurrent medications are prohibited during the study. The sponsor must be notified in advance (or as soon as possible thereafter) of any instances in which prohibited therapies are administered.

- Any anti-cancer medication (other than TRC253)
- Experimental or investigational therapy

-
- Chronic doses of corticosteroids in excess of 10 mg daily of prednisone or equivalent is prohibited other than for the management of adverse events.
 - Immunosuppressant agents
 - Vaccination with live vaccines

9.3. Precautions with Concomitant Medications

TRC253 was not an *in vitro* inhibitor of CYP1A2, 2C9, 2C19, 2D6, 3A4 or a time-dependent inhibitor of CYP 3A4, and thus has a low drug-drug interaction risk as a perpetrator. TRC253 is a low CYP-mediated clearance compound. However, strong inducers or inhibitors of CYP enzymes should be used with caution in patients receiving TRC253.

Medications that prolong the QT/QTc interval should be avoided when possible. Refer to a list of common medications that may prolong the QT interval in [Appendix 6](#).

10. TREATMENT COMPLIANCE

Patients will receive instructions on compliance with study drug administration at the screening visit. During the course of the study, the investigator or designated study-site personnel will be responsible for providing additional instruction to re-educate any patient who is not compliant with taking the study drug. All dosing information must be recorded in the Dosage Administration page of the electronic case report form (eCRF).

10.1. Patient Enrollment

Sites must assign a 6-digit screening number for patients as follows: 4-digit site number (assigned by TRACON) followed by 01, 02, etc., sequentially. Once eligibility is confirmed, patients will be manually enrolled by TRACON Pharmaceuticals and assigned an eight-digit patient number (4-digit site number followed by 4 digits). This 8-digit number will be used to identify patients throughout their participation in the trial.

11. ASSESSMENT OF EFFICACY

Efficacy evaluations include PSA response, time to PSA progression, and rPFS. For efficacy evaluation time points, see the Schedules of Assessments ([Table 7](#) and [Table 8](#)).

11.1. Disease Outcome Assessments

Outcomes in this study will be assessed using the PCWG3 criteria ([Appendix 2](#), [Appendix 3](#)).

11.2. PSA Response and Time to PSA Progression

Prostate-specific antigen will be assessed at Day 1 of each cycle and PSA response and Time to PSA Progression will be determined by PCWG3 criteria.

11.3. Radiographic Progression-Free Survival (rPFS)

The frequency of tumor assessments (soft tissue disease and bone disease assessments) is every 8 weeks until the patient completes three 28-day cycles, then every 12 weeks. Only the status of the patient's disease (partial response, stable disease, or progressive disease) based on the investigator's assessment will be recorded.

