4.2. Secondary Endpoints

- PK parameters: maximum observed plasma concentration for each patient (C_{max}), observed plasma concentration at end of a dosing interval for each patient (C_{min}), time of maximum observed plasma concentration (t_{max}), area under the plasma concentration-time curve from time zero to 24 hours at steady state (AUC_{τ}), area under the plasma concentration-time curve from time zero to the last time measured (AUC_{last}), area under the plasma concentration-time curve from time zero extrapolated to infinite time (AUC_{∞}), apparent terminal elimination rate constant (λ_z), effective half-life ($t_{1/2eff}$), terminal half-life ($t_{1/2term}$), accumulation index (R_A), total apparent oral clearance (CL/F), and apparent oral volume of distribution at steady state (V_{ss}/F)
- Mean (90% confidence interval [CI]) change in QTcF at C_{max} and slope (90% CI)
- Time to PSA progression according to PCWG3 ([Appendix 2](#))
- Radiographic PFS (rPFS) according to PCWG3 ([Appendix 3](#))
- Central read of QTcF interval in part 2

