14.3. Endpoint Definitions

PSA Response at Week 12

PSA response is defined as a $\geq 50\%$ decline from baseline according to PCWG3 criteria ([Appendix 2](#)). An additional PSA obtained at least 4 weeks later must show $\geq 50\%$ decline from baseline to confirm the response.

Time to PSA Progression

Time to PSA progression is measured from the start of treatment until the criteria for PSA progression according to the PCWG3 are met ([Appendix 2](#)). Patient without PSA progression will be censored at the last PSA assessment.

Radiographic Progression-Free Survival (rPFS)

Radiographic Progression-Free Survival (rPFS) is measured from the start of the treatment until the criteria for radiographic disease progression are met or death occurs, whichever is first. Patient will be censored at the last disease assessment when no rPFS event is observed.

Pharmacokinetic Parameters

Pharmacokinetic parameters of TRC253 will be derived from plasma concentration versus time data after single dose and repeat dose, as applicable. The pharmacokinetic parameters to be assessed are shown below. Other parameters may also be assessed.

C_{max}	Maximum observed plasma concentration for each patient
C_{min}	Observed plasma concentration at the end of dosing interval for each patient
t_{max}	Time of maximum observed plasma concentration
AUC_{τ}	Area under the plasma concentration-time curve from time zero to 24 hours (dosing interval) at steady state
AUC_{last}	Area under the plasma concentration-time curve from time zero to the last time measured
AUC_{∞}	Area under the plasma concentration-time curve from time zero extrapolated to infinite time calculated as $AUC_{last} + C_{last}/\lambda_z$, where C_{last} is the last observed measurable (non-BQL) concentration; extrapolations of more than 20.00% of the total AUC are reported as approximations
λ_z	Apparent terminal elimination rate constant, determined by linear regression using the terminal log-linear phase of the log transformed concentration vs. time curve
$t_{1/2term}$	Apparent terminal elimination rate constant, determined by linear regression using the terminal log-linear phase of the log transformed concentration vs. time curve

$t_{1/2\text{eff}}$	Effective half-life
R_A	Accumulation Index
CL/F	Total apparent oral clearance
V_{ss}/F	Apparent oral volume of distribution at steady state

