- Endpoints for delay/prevention/progression:
 - After decline from baseline: record time from start of therapy to first PSA increase that is $\geq 25\%$ and ≥ 2 ng/mL above the nadir, and which is confirmed by a second value ≥ 3 weeks later (i.e., a confirmed rising trend); the requirement for an increase of 5 ng/mL was decreased to 2 ng/mL, and the requirement for a 50% increase was reduced to 25%
 - Standards for reporting PSA progression date may not indicate a need to stop treatment
- Recording the duration of PSA decline is of little value
- No decline from baseline:
 - PSA progression $\geq 25\%$ increase and ≥ 2 ng/mL increase from baseline beyond 12 weeks
- Relate to mechanism of drug and anticipated timing of potential favorable/unfavorable effects on PSA, if present

APPENDIX 3. OUTCOME MEASURES FOR CLINICAL TRIALS IN PROSTATE CANCER: RESPONSE BY DISEASE MANIFESTATION ACCORDING TO PCWG3 [8]

General	
Endpoints for control/relief/elimination	Record changes in lymph nodes, lung, liver, adrenal, and CNS sites separately
	Record up to five lesions per site of disease.
	Record changes in size using waterfall plot.
	Use RECIST 1.1 with caveats: 
 • Confirm favorable change with second scan. Record changes in size using waterfall plot • Record complete elimination of disease at any site separately. Confirm favorable change with second scan • Record complete elimination of disease at any site separately
Nodes	
Only report changes in lymph nodes that were ≥ 1.5 cm in the short axis	
Record changes in pelvic (regional) nodes and extrapelvic (distant/metastatic) nodes separately	
Visceral	
Use RECIST 1.1 with caveats: 
 • Record changes in liver, lung, adrenal, and CNS separately • Only report changes in lesions ≥ 1.0 cm in the longest dimension 	
Nodal and Visceral	
Endpoints for delay/prevention/progression	Record changes in nodal and visceral (lung, liver, adrenal, and CNS) disease separately
	Use RECIST 1.1 but clearly record type of progression (growth of existing lesions and development of new lesions) separately by site The recommendations apply to both non-metastatic CRPC and metastatic CRPC
	Record up to five lesions per site of spread
	Report the proportion who have not progressed at fixed time points (6 or 12 months)
	Note that for some treatments, a lesion may increase in size before it decreases

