Nodal	Previously normal (<1.0 cm) lymph nodes must have grown by ≥ 5 mm in the short axis from baseline or nadir and be ≥ 1.0 cm in the short axis to be considered to have progressed
	Nodes that have progressed to 1.0 to less than 1.5 cm are pathologic, subject to clinical discretion, and nonmeasurable
	For existing pathologic adenopathy (≥ 1.5 cm), progression is defined per RECIST 1.1
Bone Metastatic	
Endpoints for control/relief/elimination	Record changes as improved or stable (no new lesions) or worse (new lesions) or resolved bone lesion
	Changes in intensity of uptake alone do not constitute progression or regression
	No new lesions: continue therapy in absence of other signs of progression

Endpoints for delay/prevention/progression	Exclude pseudoprogression in the absence of symptoms or other signs of progression
	At least two new lesions on first post-treatment scan, with at least two additional lesions on the next scan (2+2 rule) If at least two additional new lesions are seen on the next (confirmatory) scan, the date of progression is the date of the first post-treatment scan, when the first two new lesions were documented
	For scans after the first post-treatment scan, at least two new lesions relative to the first post-treatment scan confirmed on a subsequent scan
	Date of progression is the date of the scan that first documents the second lesion

Abbreviations: CNS = central nervous system; CRPC = castration-resistant prostate cancer; RECIST = Response Evaluation Criteria in Solid Tumors.

Source: Scher HI, Morris MJ, Stadler WM et al. Trial design and objectives for castration-resistant prostate cancer: updated recommendations from the Prostate Cancer Clinical Trials Working Group 3. J Clin Oncol. 2016; 34(12):1402-1418. [8]

**APPENDIX 4. NATIONAL CANCER INSTITUTE (NCI) COMMON
TERMINOLOGY CRITERIA FOR ADVERSE EVENTS
(CTCAE)**

The NCI CTCAE (Version 4.03) should be used to assess Adverse Events and may be reviewed on-line at the following NCI website:

https://evs.nci.nih.gov/ftp1/CTCAE/CTCAE_4.03_2010-06-14_QuickReference_8.5x11.pdf

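### Section 11.3 records only PR/SD/PD status, so the bone component of rPFS and its date cannot be derived or verified in the database under the PCWG3 rule the protocol names

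*Combined protocol and SAP*

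**What the plan says.** Section 4.2 lists "Radiographic PFS (rPFS) according to PCWG3" among the secondary endpoints and points to Appendix 3. Section 11.1 applies the same criteria generally: "Outcomes in this study will be assessed using the PCWG3 criteria".

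Section 11.3 then limits what is kept from each tumor assessment: "Only the status of the patient's disease (partial response, stable disease, or progressive disease) based on the investigator's assessment will be recorded".

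Appendix 3 asks for more than a status:

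- **Bone, first post-treatment scan:** "At least two new lesions on first post-treatment scan, with at least two additional lesions on the next scan (2+2 rule". If the next scan confirms, "the date of progression is the date of the first post-treatment scan".
- **Bone, later scans:** "at least two new lesions relative to the first post-treatment scan confirmed on a subsequent scan". The date is that of the scan on which the second lesion was first documented.
- **Nodal and visceral disease:** "clearly record type of progression (growth of existing lesions and development of new lesions) separately by site".

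Section 14.3 runs rPFS "until the criteria for radiographic disease progression are met or death occurs, whichever is first", and otherwise censors at the last disease assessment. Its rPFS paragraph cites no appendix and does not mention confirmation, back-dating or unconfirmed bone lesions. Section 14.8 reports rPFS by cohort only if the data suffice.

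**The concern.** The word *only* in Section 11.3 excludes the items on which the Appendix 3 bone rule operates. A recorded PD does not show whether it came from bone or soft tissue, how many lesions were new, whether a later scan confirmed them, or which scan sets the date. The status list also has no value for new bone lesions awaiting confirmation. A site that waits may enter stable disease at the first scan and PD at the confirming scan. The database would then hold the later date, although Appendix 3 requires the earlier one, and nothing in it would reveal the discrepancy.

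At stake is whether the cohort rPFS estimates represent the endpoint the protocol names. The cohorts are small (up to 15, 30 and 15), so a few such patients can be visible in the result.

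**Working it through.** The documents state no rPFS figure, so there is none to reproduce. The check has three parts.

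**1. What the bone rule needs and what is recorded**

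| Needed by Appendix 3 | Held in a PR/SD/PD status |
|---|---|
| Site and type of progression | No |
| Number of new bone lesions | No |
| Comparison with the first post-treatment scan | No |
| Confirmation on a later scan | No |
| Date of the scan first documenting the lesions | Only if the site applied the rule and dated PD back |

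**2. Scan timing (from the documents)**

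Table 8 puts Part 2 scans at Day 1 of Cycles 3, 6 and 9, with 28-day cycles. Days after first dose are (cycle − 1) × 28:

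- Cycle 3: 2 × 28 = 56 days, Week 8
- Cycle 6: 5 × 28 = 140 days, Week 20
- Cycle 9: 8 × 28 = 224 days, Week 32

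The gap from first to confirming scan is 140 − 56 = 84 days, or 12 weeks. With a window of ±7 days on each scan it is 70 to 98 days, or 10 to 14 weeks. In Part 1, Cycle 1 lasts 7 days and scans fall at Cycles 4 and 7: 7 + 2 × 28 = 63 days (Week 9) and 7 + 5 × 28 = 147 days (Week 21). The gap is again 84 days.

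One Part 2 patient with new bone lesions at Week 8 can thus appear as:

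- an event at Week 8 (Appendix 3 date, if confirmed);
- an event at Week 20 (dated at confirmation);
- censored at Week 8 (never confirmed, literal reading of Section 14.3 with Appendix 3).

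Without censoring, moving one patient shifts an event-free rate by 1/15 = 6.7 points or 1/30 = 3.3 points.

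**3. Cohort effect (assumed inputs)**

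Assume exponential rPFS with median m weeks, a share b of progressions in bone only, nobody leaving early, and a share q of the confirmed bone-only progressions dated at the confirming scan. The event-free rate at Week 20 is 2^(−20/m) with Appendix 3 dating. With q = 1 it is (1 − b) × 2^(−20/m) + b × 2^(−8/m). The shift is q × b × [2^(−8/m) − 2^(−20/m)].

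| m | b | Appendix 3 date | All at confirming scan |
|---|---|---|---|
| 24 | 0.50 | 56% | 0.5 × 0.561 + 0.5 × 0.794 = 68% |
| 16 | 0.75 | 42% | 0.25 × 0.420 + 0.75 × 0.707 = 64% |
| 32 | 0.25 | 65% | 0.75 × 0.648 + 0.25 × 0.841 = 70% |

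For m = 24 and b = 0.5 the shift is q × 0.5 × (0.794 − 0.561), about 12 points at q = 1 and about 3 points at q = 0.25.

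A simulation of that case let half of the patients with PSA progression leave treatment (further assumptions: PSA median 12 weeks, correlation 0.4 with rPFS). The Week 20 shift was about 8 points at q = 1 and about 2 at q = 0.25. At Week 32 the event-free rate was 41% with unconfirmed last-scan lesions censored and 39% with them counted as events.

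**The case against.** **The dating rule is already in the protocol.** Section 4.2 ties rPFS to Appendix 3, and Appendix 3 gives the date. This stands. A reader might infer that the plan leaves open which scan sets the date, but it does not; dating at the confirming scan would be a departure. The remaining problem is that the recorded data would not show the departure.

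**rPFS can still be computed.** A reader might infer that rPFS as a whole cannot be derived. The documents do not support that. Deaths and investigator-called soft-tissue progression give dated events without the bone rule, and a site that applies Appendix 3 correctly will record a correct PD date. The defect is confined to the bone component and its verification.

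**Source records allow checking.** Sections 15 and 18.1 require CRF data to be verifiable in source and give the sponsor and regulators access. So it would be wrong to infer that the endpoint is beyond audit. The gap is in the database.

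**Unconfirmed lesions have an implied answer.** Without confirmation the Appendix 3 criteria are not met, so Section 14.3 read literally censors the patient. This stands, but it is unwritten, and it fails if the investigator has already entered PD. Such cases can arise: the End of Treatment scan is waived if one was done within 28 days, and Table 8 has no scan at Follow-Up.

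**Another document may fill the gap.** Section 14 defers details to a Statistical Analysis Plan. Neither a separate plan nor the eCRF is among the documents, so this cannot be judged. An analysis plan could not, however, use lesion counts that Section 11.3 says are not recorded.

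**Conclusion.** The conflict between Section 11.3 and Appendix 3 is textual and needs no assumptions. From the recorded status alone, the bone component of rPFS and its date cannot be derived or verified. What the documents fix is the possible dating error for one patient: 12 weeks, or 10 to 14 with the windows.

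The cohort effect is not fixed by the documents. The shifts of 5 to 22 points at Week 20 (65% to 70%, up to 42% to 64%) rest on an assumed median and bone-only share, on nobody leaving, and on every confirmed bone-only progression being misdated. They are upper figures for each scenario; with a quarter misdated the central case falls to about 3 points. A reader might also infer that rPFS will be biased in a known direction once early withdrawal is considered. The documents do not determine its net sign or size.

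rPFS is secondary and descriptive, with no hypothesis test, so no decision rule is affected. The change should still be made, because a stated recording rule can give a wrong event date and the correction is cheap.

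**What to change.** 1. Amend Section 11.3 so that the eCRF captures, at each scan, the scan date, site and type of progression, number of new bone lesions, and whether earlier new lesions are confirmed. Back-enter these items from existing scan reports for patients already enrolled (22 in Part 1 and 12 in Part 2 per Section 2.4).
2. Derive the bone progression date by the Appendix 3 rule, and cite Appendix 3 in the rPFS paragraph of Section 14.3.
3. As a clarification, state in Section 14.3 that new bone lesions first seen on the last scan and never confirmed are censored, which is the literal reading of the present text. Show the result with them counted as events alongside.

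The cost is a few eCRF fields filled from scans already read, limited back-entry, a few sentences, and one additional rPFS result. No new scans are needed.

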12. ASSESSMENT OF SAFETY

12.1. Safety Parameters

Safety assessments will be based on medical review of adverse event reports and the results of clinical laboratory tests, ECGs, vital sign measurements, and physical examinations. For safety evaluation time points, see the Schedules of Assessments ([Table 7](#) and [Table 8](#)).

Safety parameters will be evaluated by 2 different safety committees: the TRACON Safety Monitoring Committee (SMC) and the Independent Safety Committee (ISC); refer to [Section 12.4](#).

12.1.1. Adverse Events

Adverse events that occur between the signing of the informed consent through 28 days following the last dose of study drug will be recorded. All patients who receive at least 1 dose of study drug will be considered evaluable for safety assessment. Any clinically relevant changes occurring during the study must be recorded on the Adverse Event section of the eCRF.

Adverse events reported by the patient (or, when appropriate, by a caregiver, surrogate, or the patient's legally acceptable representative) during the study will be followed by the investigator as specified in [Section 12.3](#), Adverse Event Reporting.

Abnormal and clinically significant laboratory tests should be recorded as adverse events. To meet the definition of clinically significant, the test result generally requires a change in medical management (e.g., new medication, unplanned treatment, additional tests, etc.).

